5.3 Description of Study Procedures

Patient Cohort

The study involves the participation of patients at multiple time points. The study procedures will assess the patients sexual function using the FSFI prior to the APP sexual health visit and post APP sexual health visit and telephone follow up call. Patients will be recruited through clinical chart identification.

This study involves the participation of registered nurses at multiple time points. The study procedures will assess the nurses' knowledge and confidence using the KAP and EPSE survey before sexual health program and again post education at the end of the study. The survey results will remain anonymous for both the pre and post-test. Nurse subjects will be recruited via email, and staff weekly huddles to complete both surveys.

Medical Record/Clinical Record Review:

Patient Cohort

This study involves review of medical records of patients included in this study. The questionnaire will be administered once at baseline (prior to the APP visit) and at the end of the study (after the telephone follow up call performed 8-10 weeks post APP visit). The study will collect sensitive information. This information is routinely collected per standard of care as as part of clinical care on a regular basis. A study code will be included on the questionnaire. The questionnaire will not be linked to each other and will be administered at two different time points.

- Female Sexual Function Index (FSFI)
 - o The FSFI is a validated tool that addresses five domains: desire, subjective arousal, lubrication, orgasm, satisfaction, and pain/discomfort. It encompasses nineteen self-measurement items that provides a score on overall levels of sexual function (Meston et al., 2020).
- Chart review to count the number of referrals and treatments for sexual dysfunction before and after the nurse led sexual health clinical program intervention

Nurse Cohort- N/A

Education:

Nurse Cohort

- The educational content will come from the After Cancer Solutions for Sexual Health Program, a non-profit developed with input from a cancer survivor and specialists to provide evidence-based education for providers and patients (After Cancer, 2025). The program, including the "About Us" pilot and "30 Second Message Workshop," is active across Iowa and aims to normalize sexual health discussions, build provider confidence, and guide appropriate referrals (After Cancer, 2025).
 - o 30 second message workshop

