6.2 Time Period of Data under Review

- Data will be collected from/at the following time points: 1-2 times a week from September 2025 to April 2026.
- Information will be kept for no longer than 1 year.

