8.3 Statistical Analysis Methodologies

Patient Cohort

- This pilot study will obtain estimates of the following parameters:
- The patient subjects will be, at most, 35 subjects due to the available population and limited timeframe.

- In this survey/questionnaire study, we will assess patients' sexual function in aggregate form.
- The FSFI addresses five domains to include desire and subjective arousal, lubrication, orgasm, satisfaction, and pain/discomfort. It encompasses nineteen self-measurement items that provides a score on overall levels of sexual function (Meston et al., 2020). A Likert scale is used from 1 to 5, with higher scores indicating greater levels of sexual function on the specific item. FSFI is scored in two ways; individual domains and total FSFI score by taking a sum of all scores (Meston et al., 2020).
- We hypothesize that 30% of participants have an improvement in FSFI scores indicated by a ½ standard deviation.
- The project will utilize both QI Macros and Intellectus Statistics to measure the changes in patient sexual function. The analysis will incorporate statistical methods such as run charts, control charts, and t-tests to assess sexual function in patients before and after the intervention. More specifically regarding t-tests with the FSFI tool, we will compare pre and post intervention using paired t-tests.

- The nurse subjects will be at most five.
- In this survey/questionnaire study, we will assess nurses' responses in aggregate form. The KAP survey is comprised of 24 items, each assessed using a 4-point likert scale (Xie et al., 2023).
- Participants evaluate their knowledge and skills on a scale ranging from 1 (inadequate) to 4 (more than adequate). Similarly, they rate the frequency of their practice for each item, from 1 (never) to 4 (almost always). Scores for each subscale, knowledge, attitudes, and practices, range from 24 to 96 (Xie et al., 2023). The total score for the KAP survey is obtained by summing the scores across all subscales, with higher scores indicating greater levels of knowledge, more positive attitudes, and more consistent practices (Xie et al., 2023).
- We hypothesize that 50% of nurses have an increase in KAP scores indicated by a ½ standard deviation.

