- In the next survey, EBPSE, we will assess nurses' responses in aggregate form. The EBPSE survey is comprised of 17 items designed to help nurse process information and develop essential EBP skills. Each item is rated on how confident one can perform the activity with percentage numbers 0-100 likert scale (Tucker et al., 2009).
- We hypothesize that 50% of nurses have an increase in EBPSE scores indicated by a ½ standard deviation.
- The project will utilize both QI Macros and Intellectus Statistics to measure the changes in nurses' knowledge and self-efficacy. The analysis will incorporate statistical methods such as run charts, control charts, and t-tests to evaluate changes in participants' knowledge and self-efficacy. More specifically regarding t-tests, the EBPSE will use a paired sample t-test, and the KAP survey will use t-tests to compare pre and post survey responses.

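### Run charts and control charts are listed as ways to assess change in FSFI, KAP and EBPSE, but each is measured only twice, so the charts add no sound evidence beside the t-test

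*Protocol*

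**What the plan says.** For patients, section 8.3 says the analysis will include "run charts, control charts, and t-tests to assess sexual function in patients before and after the intervention". For nurses it gives the same three tools: "run charts, control charts, and t-tests to evaluate changes in participants' knowledge and self-efficacy". It then narrows the FSFI comparison: "we will compare pre and post intervention using paired t-tests". EBPSE is also given a paired t-test, and KAP a t-test not described as paired.

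The measurement schedule is short. Section 5.3 states: "The questionnaire will be administered once at baseline (prior to the APP visit) and at the end of the study". The schedule of events in 5.1 agrees, with one FSFI at screening and one 8-10 weeks after Visit 1. The Protocol Summary puts nurses at two time points, before and after education. On the level of analysis, 8.3 says "we will assess patients' sexual function in aggregate form", and nurse responses are treated likewise. Section 8.2 caps the study at 35 patients and five nurses. No plotted unit, time interval or signal rule is given for either chart.

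Two statements in 5.3 bear on the pairing. Of the FSFI it says: "The questionnaire will not be linked to each other and will be administered at two different time points", although the questionnaire is to carry a study code. Of the nurse surveys it says that results stay anonymous at both times.

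**The concern.** Run charts and control charts judge change against a time-ordered series, which supplies the median or limits and is long enough for a run to form. A score taken once before and once after gives no such series. Section 8.3 nevertheless names the charts in the same sentence as the t-tests, for the same question.

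Two things are at stake. A chart with no signal could be set against a t-test that shows a gain, and read as evidence that the program did not work. Conversely, each extra signal rule read beside the t-test is another chance to declare a change when there was none.

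**Working it through.** The protocol gives no power figure or chart rule to reproduce.

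**Inputs from the protocol.** 35 patients with 80% completing (section 8.1): 0.80 × 35 = 28 pre-post pairs. At most five nurses (8.2). Two measurements per instrument.

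**Assumptions.** Mean shift of 0.5 SD, normal scores, pre-post correlation r of 0.3 to 0.7, two-sided 5% t-test. The protocol states none of these. It uses ½ SD only as a threshold for individual improvement.

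**1. Two aggregate points.** Let the values be x₁ and x₂, with moving range MR = |x₂ − x₁|. The centre line is their mean, so each point lies 0.5 × MR from it. Individuals-chart limits lie 2.66 × MR from it. Since 0.5 < 2.66 whatever MR is, no point can fall outside. A run of six or eight cannot occur in two points.

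**2. Patient order, 28 baselines then 28 post scores.** This is the layout most favorable to the charts.

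- *3-sigma rule, limits known.* With a 0.5 SD shift, the chance per point is P(Z > 2.5) + P(Z < −3.5) = 0.00621 + 0.00023 = 0.00644. Over 28 points, 1 − (1 − 0.00644)^28 = 0.166. With no shift, the chance per point is 0.0027, and 1 − (1 − 0.0027)^28 = 0.073.
- *3-sigma rule, limits estimated from the 28 baselines* (simulation): about 20-25% with the shift, 9-15% without.
- *Run of eight post scores above the baseline median* (simulation): about 37% with the shift and 7% without, if pre and post scores are independent. With r of 0.3 to 0.7 the figures are 35-36% and 4-6%.
- *Run of six* (simulation): 64-67% with the shift, 18-22% without.

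**3. Paired t-test on the same 28 pairs.** The standardized effect is 0.5 / √(2(1 − r)), and the noncentrality is that times √28.

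| r | standardized effect | noncentrality | power |
|---|---|---|---|
| 0.3 | 0.423 | 2.24 | 58% |
| 0.5 | 0.500 | 2.65 | 72% |
| 0.7 | 0.645 | 3.42 | 91% |

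**4. Reading them together** (simulation, 3-sigma limits estimated from the baselines, plus the 8-point run).

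- No true change: the chance that the t-test or either chart rule signals is about 16-23%, against 5% for the t-test alone. The figure varies with r and with how sigma is estimated.
- True 0.5 SD shift, sigma from the baseline SD: the t-test is significant while neither chart rule signals in about 21%, 31% and 45% of studies at r = 0.3, 0.5 and 0.7.

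**5. Calendar order.** Patients are identified as they are scheduled into clinic, and the second FSFI follows 8-10 weeks after Visit 1. If they enter over more than that interval, late baselines fall among early post scores and the chart has no clean break.

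**6. Nurses.** Two aggregate points behave as in step 1. Plotted nurse by nurse, limits would come from five baseline values, and a six-point run cannot form among five post values.

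**The case against.** The best defense is that the charts carry no weight. The list in 8.3 is introduced as illustrative, the text then assigns the FSFI comparison to the paired t-test, no decision depends on a chart, and 8.2 describes a pilot meant to inform local practice. Most of this stands and limits the harm. It does not remove the mismatch: the charts are still named as a means of assessing change in these scores, and nothing says they are only descriptive.

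A second objection is that the t-test benchmark is generous. The stated hypothesis is that 30% of patients improve by ½ SD, which is not a mean shift of ½ SD. If 30% gained exactly ½ SD and the rest nothing, the mean shift would be 0.3 × 0.5 = 0.15 SD, and paired t-test power would be about 10-17%. This is fair. The power figures above are a comparison under one assumed shift and do not show that the t-test is adequate.

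A reader might also infer more than the protocol supports:

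- *That the charts can never detect a change, or will usually show none.* The first is exact only for two aggregate points. No axis is fixed, and in patient order a 6-point run would catch a 0.5 SD shift more often than not, with many false signals.
- *That referrals and treatments form a weekly series left without an analysis.* Section 5.3 describes "Chart review to count the number of referrals and treatments for sexual dysfunction before and after the nurse led sexual health clinical program intervention", a before/after count. The phrase "1-2 times a week from September 2025 to April 2026" in 6.2 describes data collection in general and does not mention referrals. A method for these counts may sit in an analysis plan not shown.

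**Conclusion.** The point holds as a mismatch within the protocol: time-series charts are named to assess change in scores taken twice. For two aggregate points, the layout nearest the text, a signal is arithmetically impossible, and this needs no assumption. In patient order the charts either detect poorly (about 17% for 3-sigma with known limits, 37% for an 8-point run) or signal falsely too often (roughly 20% for a 6-point run). Those figures rest on 28 completers, normal scores and a 0.5 SD mean shift. The consequence is moderate, because the paired t-test carries the FSFI comparison. That test in turn depends on pre-post linkage, which 5.3 currently rules out for the FSFI and, through anonymity, leaves in doubt for the nurse surveys.

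**What to change.** In 8.3, remove run charts and control charts as methods for assessing change in FSFI, KAP and EBPSE, or state that they are descriptive only and that no signal will be interpreted. Name the mean pre-post change with its 95% CI, from the paired analysis, as the reported result.

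In 5.3, reconcile the unlinked FSFI questionnaires and the anonymous nurse surveys with the paired tests by using a study code that joins each person's two responses. Without such a code, no paired test or per-subject plot is possible.

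Optionally, keep a run chart for referral and treatment counts only, in monthly or coarser intervals, and only if a pre-program baseline series is abstracted. Weekly points would be nearly empty: at most 35 patients over about 35 weeks is one new patient a week, against 35 / 8 ≈ 4 a month.

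The cost is a wording change in 8.3 and 5.3, a code on the surveys (the FSFI already carries one), and matching text in the nurse information sheet. The optional chart adds retrospective abstraction.

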5.2 Study Design and Duration

Patient Cohort

The study design is an evidence-based practice (EBP) study and includes the implementation and evaluation of a nurse led sexual health clinical program via the FSFI survey. The duration of study participation is 12 weeks. The goal for patients is to have 80% of participating patients to complete pre and post surveys and APP visit as part of their sexual health clinical program, with 30% of patients reporting improvement in sexual dysfunction via the FSFI score.

Nurse Cohort

The study design is an EBP study and includes two surveys in the Registered Nurse participants that includes KAP and EPBSE. The duration of study participation is 4 weeks. The goal is to have 100% of the gynecology oncology registered nurses to participate in the survey and sexual dysfunction education.

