8.0 Sample Size and Statistical Considerations

8.1 Sample Size

o This is a single-site study at Cedars-Sinai.

Patient Cohort

- o The sample size of the study will vary between patient subjects.
- The patient data will depend on the number of Gynecological Oncology patients in the outpatient cancer center who have completed treatment in the past 12 months. The goal is to recruit 35 patient participants with 80% completing the pre survey, APP visit, and post survey. Goal of 30% participating patients to report improvement in sexual dysfunction via the FSFI.

Nurse Cohort

- The sample size of the study will vary between nurse subjects.
- The goal for nurse participants is to have 100% gynecological oncology outpatient registered nurses' participation in the pre surveys, sexual health education program, and post surveys.

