8.2 Statistical Sample Size Justification

A statistical sample size is not required because this study involves:

- A pilot study with at most five nurse participants'
- A pilot study with at most 35 patient subjects

 \square Waiver of a sample size justification from the IRB requested due to the following:

- This is an evidence-based practice (EBP) project to inform practice change, not generate generalizable knowledge.
- The sample size is based on the available population within a limited timeframe.

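### The patient hypothesis is a share (30% gaining ½ SD on the FSFI), but the only test named is a paired t-test of the mean change, which does not address that share

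*Protocol*

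**What the plan says.** The protocol expresses the patient target as a proportion in three places.

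- Section 5.2: "with 30% of patients reporting improvement in sexual dysfunction via the FSFI score".
- Section 8.1: "Goal of 30% participating patients to report improvement in sexual dysfunction via the FSFI".
- Section 8.3, the only place with a threshold: "We hypothesize that 30% of participants have an improvement in FSFI scores indicated by a ½ standard deviation".

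For methods, section 8.3 says: "The analysis will incorporate statistical methods such as run charts, control charts, and t-tests to assess sexual function in patients before and after the intervention". It then becomes specific: "More specifically regarding t-tests with the FSFI tool, we will compare pre and post intervention using paired t-tests". No count, interval or test of a proportion is named. Section 8.3 also opens by promising estimates of parameters, but the bullets that follow name none.

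On numbers, section 8.1 says: "The goal is to recruit 35 patient participants with 80% completing the pre survey, APP visit, and post survey". Section 8.2 describes "A pilot study with at most 35 patient subjects" and makes no power claim. The protocol does not give a significance level, the SD that the ½ SD refers to, or a pre-post correlation.

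**The concern.** The hypothesis asks how many individual patients improve by a stated amount. A paired t-test asks whether the average change is zero. A share of 30% improvers can sit beside a mean change near zero if other patients worsen or scores fluctuate. A clear mean gain can also arise from many small improvements, with few patients reaching ½ SD.

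If the analysis is run as described, the report will contain a p-value that does not answer the stated hypothesis. The share, if reported at all, would be a bare percentage with no statement of its precision. A reader who took the p-value as the answer to the 30% goal could be misled in either direction.

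**Working it through.** The plan gives no power figure or calculated sample size, so there is nothing of its own to reproduce beyond the completer count.

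**Inputs from the protocol.** Up to 35 recruited and 80% completing (8.1): 0.80 × 35 = 28 pairs. Target share 30%, threshold ½ SD (8.3).

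**Assumptions, because the protocol is silent.** Two-sided 5% level; normally distributed changes; equal pre and post SDs, set to 1; pre-post correlation *r* varied.

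**Step 1: the mean change implied by a share of exactly 30%.**

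SD of change = √(2(1 − r)). For 30% to exceed 0.5, the mean change must be 0.5 − 0.524 × SD of change, where 0.524 is the 70th percentile of the standard normal.

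**Step 2: the chance of a significant improvement.** Noncentral t with 27 df, critical value 2.052, noncentrality (mean / SD of change) × √28. At r = 0.7: SD of change = √0.6 = 0.775; mean = 0.5 − 0.524 × 0.775 = 0.094; standardised mean = 0.121; noncentrality = 0.121 × 5.29 = 0.64; power = 9%.

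| r | SD of change | implied mean | significant improvement, n = 28 | n = 35 |
|---|---|---|---|---|
| 0.5 | 1.000 | −0.024 | 1.9% | 1.8% |
| 0.7 | 0.775 | 0.094 | 9.0% | 10.3% |
| 0.8 | 0.632 | 0.168 | 27% | 33% |
| 0.85 | 0.548 | 0.213 | 51% | 61% |
| 0.9 | 0.447 | 0.265 | 86% | 93% |

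**Step 3: other readings of the hypothesis.**

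- If ½ SD means the SD of the change score, the standardised mean is 0.5 − 0.524 = −0.024 and the figure is 1.9% (n = 28).
- If 30% gain exactly ½ SD and the other 70% do not change at all, simulation (40,000 runs) gives 98% (n = 28).

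**Step 4: the converse.**

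- At r = 0.95 and a mean gain of 0.2 SD, the SD of change is 0.316. The share reaching ½ SD is 1 − Φ((0.5 − 0.2)/0.316) = 17%, yet the t-test is significant in about 90% of trials (n = 28).
- With no mean change at all, 1 − Φ(0.5) = 31% still reach ½ SD of the change score, or ½ baseline SD at r = 0.5.

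**Step 5: precision of the share itself (Clopper-Pearson 95%).** 30% of 28 is 8.4 patients, so 8 and 9 bracket the goal.

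- 8/28 = 28.6%, interval 13.2% to 48.7%.
- 9/28 = 32.1%, interval 15.9% to 52.4%.

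**The case against.** The paired t-test has its own job. Section 3.0 sets out to evaluate whether the program improves sexual dysfunction as measured by the FSFI, and a pre-post mean comparison speaks to that. The protocol calls the 30% a goal, lists its methods as examples, describes a pilot, and never says that the t-test decides the 30%. An analysis plan that is not shown could add the proportion.

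Much of this stands. The t-test should be kept, no power is owed, and the choice of interval method could reasonably sit in an analysis plan. What remains is that section 8.3 itself states a hypothesis, itself names a test, and the two concern different quantities. Pilot status excuses the absence of a sample size calculation. It does not excuse leaving the stated hypothesis without an analysis.

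A reader might go further and infer that the t-test would usually be non-significant when the hypothesis is true, so that the report would reject a goal that had been met. The protocol does not support this. The first half holds under normal changes if ½ SD refers to the change score, or to the baseline SD with a correlation below about 0.85 (n = 28). It fails at higher correlations, or if non-improvers stay unchanged. The second half needs a decision rule that the protocol never states.

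**Conclusion.** The mismatch holds: section 8.3 does not analyse its own patient hypothesis. When the share is exactly 30%, the chance of a significant improvement ranges from about 2% to about 98% over the cases shown for 28 completers. That spread reflects the unstated SD, correlation and distribution of change, as well as an assumed two-sided 5% level. It is not a prediction that the test will fail. It shows that the t-test carries no fixed information about the 30% goal in either direction.

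The share can be estimated only roughly, to about ±18 points with 28 completers. It would be too strong to say that the data could exclude neither 15% nor 50%: the interval for 8/28 excludes 50%, and the one for 9/28 excludes 15%. The supportable statement is that the estimate is imprecise and the 30% serves as a benchmark. The point is worth correcting before analysis, but it is moderate in weight for a pilot that makes no power claim.

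**What to change.** In section 8.3:

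1. Define the SD that the ½ SD refers to, for example the baseline SD of the FSFI total score.
2. Name the number and share of patients gaining at least ½ SD, with an exact (Clopper-Pearson) 95% CI, as the analysis of the 30% goal. Say that at about 28 completers the goal is a benchmark.
3. Keep the paired comparison as a separate estimate of mean change with its 95% CI, and state that its p-value does not decide the 30% goal.

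In section 5.3, reconcile the statement that the pre and post questionnaires will not be linked with the study code placed on them, so that each patient's two forms can be paired. Both the per-patient count and the paired t-test need this.

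The cost is a few sentences in 8.3 and one clarification in 5.3, with no new data collection proposed. The downside is a headline result that is a wide interval and looks less decisive than a p-value.

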Information sheet will be given to nurses using REDcap. Nurses will be recruited to participate in the electronic pre and or post survey and informed they may self-select to participate in the project by clicking the survey link and QR code provided to them. A waiver of documentation of informed consent is being requested. By clicking the link, this implies their consent to participate. Nurses will be informed that they may withdraw from participating in the project at any time by exiting the survey. All nurses in the Gynecology Oncology Outpatient Cancer Clinic will receive Sexual Dysfunction training. However, only nurses who agree/consent to the pre-and post-education surveys (KAP & EBPSE) will be involved in the survey.

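### Section 8.3 names a paired t-test for the EBPSE but leaves the KAP t-test unnamed, and the anonymous, uncoded nurse surveys leave no planned way to pair either scale

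*Protocol*

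**What the plan says.** Section 8.3 lists run charts, control charts and t-tests for the nurse data, then narrows the last item: "the EBPSE will use a paired sample t-test, and the KAP survey will use t-tests to compare pre and post survey responses". For the patients' FSFI, the same section specifies paired t-tests. The KAP is therefore the only before-and-after instrument whose t-test is not identified.

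The KAP hypothesis reads: "We hypothesize that 50% of nurses have an increase in KAP scores indicated by a ½ standard deviation". The EBPSE hypothesis has the same form and the same two figures.

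Both scales follow one schedule. Section 5.3 has nurses assessed "using the KAP and EPSE survey before sexual health program and again post education at the end of the study" (EPSE and EBPSE are used for the same scale). Section 4.3.1 says that "only nurses who agree/consent to the pre-and post-education surveys (KAP & EBPSE) will be involved in the survey", and Section 8.1 aims for "100% gynecological oncology outpatient registered nurses' participation in the pre surveys, sexual health education program, and post surveys". On numbers, Section 8.3 says: "The nurse subjects will be at most five".

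Four further statements bear on linkage:
- Section 5.3 keeps the nurse results anonymous at both the pre-test and the post-test.
- Section 6.3 lists age, gender, work unit, position and time in position for nurses, and no code.
- Section 6.4 assigns a unique study number to patients only.
- The recruitment wording in Section 4.3.1 lets a nurse take part in only one of the two surveys.

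**The concern.** The sentence in Section 8.3 is there to say which t-test goes with which scale. It does so for the EBPSE and not for the KAP, although the respondents and times are the same. An analyst could run either test on the KAP. With five nurses that choice can change the result, and it could be made after the data are seen.

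The choice also matters for validity. Two scores from one nurse are normally correlated. A two-sample test ignores this and takes the spread between nurses as its error term, where the spread of each nurse's change is wanted.

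Naming the paired test is not enough, however. A paired test needs each nurse's two surveys matched, and so does a count of nurses who improve by half an SD. The Protocol describes no matching. The paired EBPSE test and both hypotheses therefore conflict with the data collection in Section 5.3.

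**Working it through.** **Is there a figure to reproduce?** No. The Protocol gives no power, significance level or pre-post correlation for nurses. The numbers below illustrate what is at stake if the KAP were tested unpaired.

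**Inputs.** n = 5 nurses (the maximum in Sections 8.2 and 8.3) and a gain of ½ SD (the hypothesis threshold in Section 8.3, used here as a mean shift). Assumed: normal scores, equal SDs at both times, two-sided 5% level, and correlation ρ from 0 to 0.9.

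**Standard errors and intervals, in SD units.**
- Paired: SE = √(2(1−ρ)/n), df = n − 1 = 4, critical t = 2.776.
- Unpaired: SE = √(2/n) = √0.4 = 0.632, df = 2n − 2 = 8, critical t = 2.306. The half-width is 2.306 × 0.632 = 1.46 at any ρ.
- At ρ = 0.5 the paired SE is √(1/5) = 0.447, so the half-width is 2.776 × 0.447 = 1.24. The variance of the mean change is 0.2, while the unpaired test takes it as 0.4, twice too large.
- The widths are equal where 2.776·√(1−ρ) = 2.306, so ρ = 1 − (2.306/2.776)² ≈ 0.31. Below that the paired interval is the wider one.

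**Error rate and power.** Paired power comes from the noncentral t with df 4 and noncentrality d√n/√(2(1−ρ)), where d is the mean gain in SD units; for d = 0.5 and ρ = 0.5 this is 0.5 × 2.236/1 = 1.118. The unpaired test was simulated on the same correlated data (200,000 data sets per setting).

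| ρ | False-positive rate, unpaired | Power at ½ SD, paired | Power at ½ SD, unpaired | Half-width, paired | Half-width, unpaired |
|---|---|---|---|---|---|
| 0 | 4.9% | 9.5% | 10.7% | 1.76 | 1.46 |
| 0.3 | 2.6% | 11.4% | 7.9% | 1.47 | 1.46 |
| 0.5 | 1.4% | 14.1% | 6.1% | 1.24 | 1.46 |
| 0.7 | 0.5% | 20.1% | 4.4% | 0.96 | 1.46 |
| 0.9 | 0.1% | 47.7% | 2.8% | 0.56 | 1.46 |

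The paired false-positive rate is 5% throughout. At a 1 SD gain and ρ = 0.5, power is 40% paired and 25% unpaired.

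**Can the surveys be paired?** Set side by side, Section 8.3 requires matched EBPSE scores, Section 5.3 makes both surveys anonymous, and Sections 6.3 and 6.4 provide no nurse code. Without a link, the only t-test that can be run on either scale is a two-sample one. The share of nurses improving cannot be recovered either. If two nurses score a and b before and a and b after, the unlinked data fit no change in anyone, and equally one nurse rising and the other falling by the difference.

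**The case against.** A reader might infer that the Protocol prescribes a two-sample test for the KAP, as if the two surveys came from different nurses. It does not. The words unpaired, independent and two-sample do not appear. Section 8.3 uses t-tests as a general term for the FSFI too before making it paired, and the plural may only reflect the KAP's subscales and total. An unnamed variant could also be settled in a statistical analysis plan that is not shown. This stands, so the point is not that a wrong test has been specified. But the Protocol chose to assign tests here and did so unevenly, and a later plan could not restore a link that was never collected.

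It can also be said that the effect is small. At the Protocol's own half SD, neither test is informative unless the correlation is very high. For positive correlation an unpaired test gives too few false positives, not too many. Below a correlation of about 0.3 its interval is the narrower one. And neither t-test evaluates a share of nurses improving. All of this stands and limits the weight of the point.

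Finally, with so few nurses, surveys might be matched on age and time in position. The Protocol plans no such matching, and it would sit badly with the anonymity statement.

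**Conclusion.** The point holds in two linked parts. Section 8.3 leaves the type of KAP t-test open beside a paired test for a scale with the same design. The anonymity in Section 5.3, with no nurse code, means that the paired EBPSE test and both hypotheses on the share of nurses improving cannot be carried out as written. The second part rests on the text alone and needs no numerical assumption.

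The size of the first part depends on assumptions that the Protocol does not supply. At a correlation of 0.5, an unpaired KAP test would have a false-positive rate of about 1.4% and power of 6% against 14% for a half-SD gain. Across correlations from 0.3 to 0.7 the power contrast runs from 8% against 11% to 4% against 20%.

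Practical impact is low: at most five nurses, a secondary objective, a pilot with no power claim, and an error in the conservative direction.

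**What to change.** 1. **Section 8.3.** State one rule for both scales: *KAP and EBPSE scores will each be compared before and after the education with a paired t-test on the within-nurse change, reported with a 95% confidence interval.*
2. **Section 5.3.** Reconcile anonymity with pairing. Each nurse enters the same self-generated code on both surveys, one that the study team cannot trace to a person. Add the code to the nurse data elements in Section 6.3.
3. **Section 4.3.1.** Reconcile the wording that allows one survey only with the requirement for both, and say that a nurse with one survey does not enter the paired test.

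If pre-surveys have already been collected without a code, pairing cannot be recovered. The plan should then say so, withdraw the paired EBPSE test and the two hypotheses on the share of nurses improving, and report the scores descriptively.

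**Cost.** One sentence in Section 8.3, one extra survey field, and a small edit to the nurse survey and information sheet. Degrees of freedom fall from 8 to 4, so the paired interval is wider if the correlation is below about 0.3. Nurses with only one survey, or whose codes do not match, drop out of the test, which matters when there are at most five.
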